In another study on rats with induced endometriosis, markers such as MCs, chymase, NGF, VEGF, and Flk1 (VEGF receptor) were shown to be significantly reduced under PEA/PLD treatment. More importantly, treatment resulted in fewer episodes of uterine pain and smaller endometriotic cysts size (42). Pain was assessed by recognizing characteristic positional behavior known to be associated with uterine pain. These results in rats suggest that PEA/PLD may act both by reducing pain and by reducing lesion size and/or activity.

Study Name: Palmitoylethanolamide and polydatin effect on pain and dysmenorrhea in women scheduled for laparoscopic treatment of possible endometriosis: a double blind randomised controlled trial

Protocol Number: 1 Version 0.5, dated 29 September 2020

The aim of this study is to assess the efficacy of PEA/PLD for pain reduction in patients with endometriosis, and to investigate the effect of PEA/PLD on lesion cellular and molecular markers including MC, chymase, NGF, VEGF, and Flk1 (VEGF receptor) expression.

This study looks at the analgesic and anti-inflammatory effects of PEA/PLD on endometriosis related pain prior to and following surgical treatment. We aim to look at the difference in inflammatory markers in the endometriotic lesions, as well as in peritoneal biopsies and fluid between PEA/PLD and placebo.

4. Study Objectives

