7.2. Handling of Withdrawals

Should a participant choose to withdraw from the study no further information will be collected. If the participant withdraws prior completing 6 weeks of medical treatment, she will be removed from the study.

If the participant withdraws following the medical treatment and the second questionnaire but either prior to or after surgery, she will be asked if the data collected prior to their withdrawal is able to be used. Should they decline the data will be removed from the data bank and stored in a separate folder to ensure it is not included in the final analysis.

If the participant falls pregnant during the medical treatment phase, she will be removed from the study.

If the participant falls pregnant after the medical treatment phase and the surgery but prior the last questionnaire she will remain in the study and complete the last questionnaire as planned.

If participants have consumed less than 80% of the treatment, they will be removed from the study.

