8.1. Sample Size Estimation & Justification

The sample size required for a one point difference on the numerical pain scale between PEA/PLD treatment and placebo in the change of each type of pain measured VAS score before (at recruitment) and at 4 months after surgery, and SD of 2 (based on a previous study performed by our team), was calculated to be 128 (64 in each group), based on an alpha of 0.05, power of 0.8 and two sided p-value. Allowing for a drop-out rate of 30%, and assuming that 30% of patients will not be found to have endometriosis on surgery, a total sample size required is 130 in each group (N=260).

If the participant withdraws prior to completing 6 weeks of medical treatment, she will be removed from the study.

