8.2. Statistical Methods to Be Undertaken

Continuous variables will be explored with summary statistics (mean, standard deviation, quartiles, range) and graphs (box plots, dot plots). Comparisons between the PEA treatment and placebo will be performed using t-tests, or Mann-Whitney U tests if appropriate.

The impact of the treatment on continuous pain measures will be assessed using linear models adjusting for the effect of covariates, including pre-treatment pain measures.

Categorical variables will be summarized as proportions and cross tabulated frequencies, and associations examined using chi-squared and Fisher's exact tests. A modified intention to treat approach to analysis will be undertaken.

9. Storage of Blood and Tissue Samples

Study Name: Palmitoylethanolamide and polydatin effect on pain and dysmenorrhea in women scheduled for laparoscopic treatment of possible endometriosis: a double blind randomised controlled trial

Protocol Number: 1 Version 0.5, dated 29 September 2020

9.1. Details of where samples will be stored, and the type of consent for future use of samples

All samples will be processed and stored within the research laboratory at the Melbourne University, Department of Obstetrics and Gynaecology, Level 7, at the Royal Women's Hospital. Samples will be deidentified and labelled with a unique tissue bank number linked to all samples collected for each patient (blood, peritoneal fluid, endometriosis lesion, endometrium and clinical data). RNA samples will be stored long term at -80°C and histology samples will be stored long term in histology block drawers. The laboratory has key card access which restricts access to research personnel only. The laboratory is also located within the Research Precinct of RWH which also has key card access further restricting access to Departmental staff only. These two measures ensure the protection of the sample storage and all data collected relating to the patient.

10. Data Security & Handling

10.1. Details of where records will be kept & How long will they be stored

Paperwork from the project will be kept in a locked room at The Royal Women's Hospital and all computerized information will be kept in a database that is password protected. Only members of the research team will have the password. All information will be kept for a period of 7 years after the project is completed, at which time hard copy records will be shredded and computer files deleted.

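### Section 7.2 removes randomised women for low intake, early withdrawal or on-treatment pregnancy, so the primary comparison as written is adherence-selected and does not fit the modified intention-to-treat approach in 8.2

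*Protocol*

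**What the plan says.** Protocol section 7.2 (Handling of Withdrawals) sets three grounds for removal that arise after randomisation:

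- Intake: "If participants have consumed less than 80% of the treatment, they will be removed from the study".
- Early withdrawal: "If the participant withdraws prior completing 6 weeks of medical treatment, she will be removed from the study". Section 8.1 repeats this within the sample-size paragraph: "If the participant withdraws prior to completing 6 weeks of medical treatment, she will be removed from the study".
- Pregnancy: "If the participant falls pregnant during the medical treatment phase, she will be removed from the study". A woman who becomes pregnant after both treatment and surgery is handled differently: "she will remain in the study and complete the last questionnaire as planned".

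Section 7.2 also says: "Should a participant choose to withdraw from the study no further information will be collected". Women who withdraw after the second questionnaire are asked whether their data may be used. No such question is described for the three groups above.

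Section 7.3 continues recruitment until each group has 130 women for the primary outcome. Section 8.2 then declares: "A modified intention to treat approach to analysis will be undertaken". The modification is not defined, and the protocol describes no analysis that includes the removed women.

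The primary outcomes (4.3.1 and 4.3.2) concern pain change before surgery in women with endometriosis. According to the lay summary (3.1), endometriosis is confirmed or excluded at surgery, which follows the 8 weeks of treatment.

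**The concern.** A modified intention-to-treat analysis normally keeps women in their allocated arm whatever they took, apart from narrow and stated exceptions. A set restricted to those who took at least 80% of treatment is a per-protocol type of set. The two descriptions do not fit together, and 7.2 is the one that would be carried out day to day.

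Intake and withdrawal happen after randomisation and may depend on both arm and pain. Section 7.1 lets a woman stop at any time for any adverse reaction, and lack of relief is another plausible reason. If the women who leave differ between arms, those who remain are no longer comparable by design, and either a positive or a negative result could partly reflect who stayed.

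Some of this loss is avoidable. Under 5.4, compliance is asked at week 8 on the same questionnaire that records pain. A woman below 80% who returns it has a recorded primary outcome, which 7.2 would then set aside.

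A smaller, related matter is that membership of the primary set also depends on a finding made after treatment. On its animal evidence, section 3.2 says: "These results in rats suggest that PEA/PLD may act both by reducing pain and by reducing lesion size and/or activity". By the protocol's own rationale, treatment could therefore influence who is classed as having endometriosis.

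**Working it through.** **1. The plan's own figure (8.1).** Inputs: difference 1 point, SD 2, two-sided alpha 0.05, power 0.80.
- Normal approximation: n = 2 × (1.96 + 0.842)² × 2² / 1² ≈ 63 per arm. The exact two-sample t-test needs 64 (power 0.801; 0.795 at 63), as stated.
- Inflation for 30% drop-out and 30% without endometriosis: 64 / (0.7 × 0.7) = 130.6, against the stated 130. Conversely, 130 × 0.49 = 63.7 evaluable per arm.

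The sample size reproduces, and this point does not depend on any error in it.

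**2. Sections 7.3 and 8.1 side by side.** Section 8.1 reaches 130 after allowing for loss, while 7.3 keeps recruiting until 130 have the primary outcome. If 30% were lost before week 8, that would need 130 / 0.7 = 185.7, or about 186 randomised per arm. Removed women are in effect replaced by women who pass the intake test.

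**3. How selection turns into bias (illustration).** Suppose there is no true effect. Let p be the proportion removed in an arm and g the amount by which removed women fare worse than retained women. The two full arms have equal means, so the retained women differ between arms by p₁g₁ − p₂g₂. All values of p and g below are assumptions; the documents give none.
- Removal rates differ by 10 percentage points, g = 2 points in both arms: 0.10 × 2 = 0.2 points.
- 30% removed in each arm, g larger by 1 point in one arm: 0.30 × 1 = 0.3 points.
- 10% removed in each arm, g larger by 1 point in one arm: 0.10 × 1 = 0.1 points.

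**4. Effect on type I error.** With 64 per arm, SE = 2 × √(2/64) = 0.354. For bias b, the two-sided error is 1 − Φ(1.96 − b/SE) + Φ(−1.96 − b/SE).

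| Bias (points) | Type I error |
|---|---|
| 0 | 0.050 |
| 0.1 | 0.059 |
| 0.2 | 0.087 |
| 0.3 | 0.136 |
| 0.5 | 0.293 |

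**5. Whether the planned number supports an as-randomised analysis.** If every woman with endometriosis had a week-8 score, 130 × 0.7 = 91 per arm would be analysed, with SE = 2 × √(2/91) = 0.297. Power = Φ(effect/SE − 1.96).

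| Average effect (points, assumed) | Power |
|---|---|
| 1.0 | 0.92 |
| 0.9 | 0.86 |
| 0.8 | 0.77 |
| 0.7 | 0.66 |

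Power stays at 80% down to an average effect of about 2.802 × 0.297 = 0.83 points. With some scores missing and imputed, it would be lower than shown.

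**The case against.** **The label is undefined and the SAP is not shown.** Section 7.2 uses explicit wording about the final analysis only for women who decline use of their data; elsewhere it speaks of removal from the study. An SAP could define the modified set so that under-80% women with a week-8 score are kept. This stands in part: that the analysis is per-protocol is a reading of the text, not something the protocol states. It is still the natural reading, and an SAP could depart from it only by overriding 7.2. For women who withdraw, it could not restore scores that were never collected.

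**Blinding and tolerability limit differential loss.** The trial is double-blind, and 7.1 cites 4 adverse events in 786 treated patients. This makes large removal driven by side effects less likely. It does not rule out removal related to lack of relief.

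**The planned 30% drop-out is not a measure of 7.2 removal.** Section 8.1 attaches it to a comparison at 4 months after surgery, so it can include later loss. This stands, and it is why the 30% in the illustration is an assumption.

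**Stronger readings that the documents do not support.**
- A reader might infer that the 6-week and 80% rules contradict each other, since 6 of 8 weeks is 75% of treatment (84 of 112 doses). One concerns withdrawal and the other intake. Nothing says that a woman who passes 6 weeks is kept whatever her intake, so the conditions are cumulative.
- A reader might infer that restricting to confirmed endometriosis invalidates the primary comparison, or try to size that bias by assuming the best responders are the ones lost. Confirmed disease is the declared target population, and women without it are compared in 4.3.5 and 4.3.6. The animal evidence concerns size or activity, not lesions becoming undetectable. Section 3.2 also cites a study in women, of a different PEA-containing product, with no change in endometrioma diameter. The protocol does not say how women who have no surgery are analysed. This supports an added analysis, not a claim of demonstrated bias.

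**Conclusion.** The point holds. Sections 7.2, 7.3 and 8.1, followed as written, give a primary comparison selected on adherence and on staying in treatment, which does not fit the approach named in 8.2. It is open to selection bias, and part of the excluded information would already be in hand.

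The size and direction of the bias cannot be derived from the documents. The rise in type I error to about 0.09 to 0.14 rests on an assumed bias of 0.2 to 0.3 points, SD 2 and 64 per arm; an assumed bias of 0.1 gives only 0.059. These figures show what modest differential removal could do, not what will happen.

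It should be settled before the data are collected, because it affects the primary comparison and week-8 scores that are not sought cannot be recovered. The dependence on surgical confirmation is secondary and calls for a supporting analysis only.

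**What to change.** 1. In 7.2 and 8.1, separate not taking or stopping capsules, for whatever reason the protocol already allows, from leaving the study and the analysis. When capsules are stopped is a clinical matter and is left as the protocol has it.
2. Seek the week-8 questionnaire from every randomised woman who has not withdrawn consent to follow-up.
3. Define the primary set as all randomised women with surgically confirmed endometriosis, by allocated arm and regardless of intake. Handle missing week-8 scores by multiple imputation. Because imputation usually assumes that loss is explained by observed data, add a sensitivity analysis for outcome-dependent loss, for example by shifting imputed scores by arm.
4. Keep the 80% set as a supplementary per-protocol analysis.
5. Reconcile 7.2, 7.3, 8.1 and 8.2: remove the 6-week exclusion from both places as an analysis rule, define the modified intention-to-treat set, and say whether 130 per group counts women randomised or women with the primary outcome.
6. Add a supporting comparison of week-8 change in all randomised women, and report by arm the proportions with endometriosis confirmed and with surgery not done.

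The cost is protocol wording and questionnaire reminders. The estimate may be somewhat diluted if adherence matters; with complete scores, the planned number keeps at least 80% power down to an average effect of about 0.83 points.

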7.3. Replacements

We will continue to recruit until we have 130 participants per group for the primary outcome. Any withdrawals after this point will not be replaced because this data is for secondary outcomes only.

8. Statistical Methods

8.1. Sample Size Estimation & Justification

The sample size required for a one point difference on the numerical pain scale between PEA/PLD treatment and placebo in the change of each type of pain measured VAS score before (at recruitment) and at 4 months after surgery, and SD of 2 (based on a previous study performed by our team), was calculated to be 128 (64 in each group), based on an alpha of 0.05, power of 0.8 and two sided p-value. Allowing for a drop-out rate of 30%, and assuming that 30% of patients will not be found to have endometriosis on surgery, a total sample size required is 130 in each group (N=260).

If the participant withdraws prior to completing 6 weeks of medical treatment, she will be removed from the study.

8.2. Statistical Methods to Be Undertaken

Continuous variables will be explored with summary statistics (mean, standard deviation, quartiles, range) and graphs (box plots, dot plots). Comparisons between the PEA treatment and placebo will be performed using t-tests, or Mann-Whitney U tests if appropriate.

The impact of the treatment on continuous pain measures will be assessed using linear models adjusting for the effect of covariates, including pre-treatment pain measures.

Categorical variables will be summarized as proportions and cross tabulated frequencies, and associations examined using chi-squared and Fisher's exact tests. A modified intention to treat approach to analysis will be undertaken.

9. Storage of Blood and Tissue Samples

Study Name: Palmitoylethanolamide and polydatin effect on pain and dysmenorrhea in women scheduled for laparoscopic treatment of possible endometriosis: a double blind randomised controlled trial

Protocol Number: 1 Version 0.5, dated 29 September 2020

9.1. Details of where samples will be stored, and the type of consent for future use of samples

All samples will be processed and stored within the research laboratory at the Melbourne University, Department of Obstetrics and Gynaecology, Level 7, at the Royal Women's Hospital. Samples will be deidentified and labelled with a unique tissue bank number linked to all samples collected for each patient (blood, peritoneal fluid, endometriosis lesion, endometrium and clinical data). RNA samples will be stored long term at -80°C and histology samples will be stored long term in histology block drawers. The laboratory has key card access which restricts access to research personnel only. The laboratory is also located within the Research Precinct of RWH which also has key card access further restricting access to Departmental staff only. These two measures ensure the protection of the sample storage and all data collected relating to the patient.

10. Data Security & Handling

10.1. Details of where records will be kept & How long will they be stored

Paperwork from the project will be kept in a locked room at The Royal Women's Hospital and all computerized information will be kept in a database that is password protected. Only members of the research team will have the password. All information will be kept for a period of 7 years after the project is completed, at which time hard copy records will be shredded and computer files deleted.

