Protocol Number: 1 Version 0.5, dated 29 September 2020

Statistical Methods:	
Continuous variables will be summarised as means with standard deviation if normally distributed or median with interquartile range if not. Comparisons will be performed using t-tests and Mann Whitney U tests respectively.
 
Categorical variables will be summarised as proportions and comparisons performed using Chi-squared and Fisher exact tests. P values of <0.05 will be considered significant.
 
The impact of the PEA treatment on continuous outcome pain measures will be assessed using linear modelling adjusting for the effect of covariates including pre-treatment pain measures.

Subgroups:	
 • Patients treated by palmitoylethanolamide/ • polydatin 400 mg/40 mg • Patients treated by placebo • Patients with surgically proven endometriosis • Patients with surgically proven absence of endometriosis

Study Name: Palmitoylethanolamide and polydatin effect on pain and dysmenorrhea in women scheduled for laparoscopic treatment of possible endometriosis: a double blind randomised controlled trial

Protocol Number: 1 Version 0.5, dated 29 September 2020

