4.3. Outcome Measures

Primary outcomes

- 4.3.1. To compare the change in dysmenorrhoea VAS score between PEA/PLD and placebo treatment in patients with endometriosis prior to laparoscopic surgical treatment.
- 4.3.2. To compare the change in dyspareunia, dyschezia and persistent pelvic pain VAS score between PEA/PLD and placebo treatment in patients with endometriosis prior to laparoscopic surgical treatment.

Secondary outcomes

- 4.3.3. To compare the change in dysmenorrhoea VAS score between PEA/PLD and placebo treatment at baseline and 4 months after laparoscopic surgery for endometriosis.
- 4.3.4. To compare the change in dyspareunia, dyschezia and persistent pelvic pain VAS score between PEA/PLD and placebo treatment at baseline and 4 months after laparoscopic surgery for endometriosis.

Study Name: Palmitoylethanolamide and polydatin effect on pain and dysmenorrhea in women scheduled for laparoscopic treatment of possible endometriosis: a double blind randomised controlled trial

Protocol Number: 1 Version 0.5, dated 29 September 2020

- 4.3.5. To compare the change in dysmenorrhoea, dyspareunia, dyschezia and persistent pelvic pain VAS score between PEA/PLD and placebo, before surgery, in patients without surgical evidence of endometriosis.
- 4.3.6. To compare the change in dysmenorrhoea, dyspareunia, dyschezia and persistent pelvic pain VAS score between PEA/PLD and placebo, at baseline and 4 months after laparoscopic surgery without evidence of endometriosis.
- 4.3.7. To compare the change of quality of life between PEA/PLD and placebo treatment in women with surgical evidence of endometriosis, before surgery and again after surgery.
- 4.3.8. To compare changes in cellular and molecular markers from endometriotic lesions, blood and peritoneal fluid samples between patients treated by PEA/PLD and placebo.
- 4.3.9. To correlate changes in VAS score with changes in cellular and molecular markers, in patients with endometriosis, treated by PEA/PLD and placebo.
- 4.3.10. To assess the side effects of PEA/PLD.

5. Study Design

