5.4. Study methodology

All subjects will be given oral and written information about the study and informed written consent will be obtained by our Research Nurses / Assistant (see attached patient information and consent forms). After consent has been obtained, an initial questionnaire will be completed by the women. The questionnaire includes demographic details, medical background, pain questions about menstrual pain and other pelvic pain symptoms including dysmenorrhoea, deep dyspareunia, dyschesia, daily pain and quality of life assessment.

Quality of life domains will include physical and mental health.

Recruited patients will then be blindly randomized to receive either PEA/PLD 400 mg/40 mg or placebo twice daily for 8 weeks.

Treatment will be prepared by a specialist compounding pharmacy in the form of similar capsules for PEA/PLD and placebo, distributed in similar containers with their content only known to the pharmacists.

The same questionnaire (without the demographic and medical history part) will then be filled at the end of 8 weeks of treatment (still before surgery) with additional adverse drug side effects and treatment compliance assessment.

Surgery will take place within 2 weeks of finishing the study treatment.

Final questionnaire will be sent to participants 4 months' after the surgery to evaluate pain and quality of life.

Collection of tissue Samples and clinical/medical Information

Only patients operated on at the Royal Women's Hospital will be consented for tissue/ biofluid collection. Patients operated at the Mercy Hospital for Women or private hospitals will have their surgeries as planned without any other surgical intervention.

Blood: During surgery, blood samples (25-50 mls, or 1¼ -2½ tablespoons) will be drawn and processed in the laboratories at the RWH.

Endometrial Biopsy: A routine endometrial biopsy will be collected from each woman. The biopsy will be collected following collection of a clinical biopsy during hysteroscopy (endometrial biopsies will only be collected from women providing clinical consent for an endometrial biopsy as part of her planned medical procedure). Endometrial samples will be histologically assessed for cycle stage and some will be stored in RNA later (Life Technologies) for mRNA (NGS analysis) or protein expression studies or used immediately in in vitro cell culture studies.

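### Quality of life (4.3.7) is measured at baseline, but the baseline-adjusted model is named only for pain; extending it to quality of life is a free, optional gain in precision

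*Protocol*

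**What the plan says.** Section 8.2 gives a general rule for continuous variables: "Comparisons between the PEA treatment and placebo will be performed using t-tests, or Mann-Whitney U tests if appropriate". It then adds a model-based analysis for one class of outcome: "The impact of the treatment on continuous pain measures will be assessed using linear models adjusting for the effect of covariates". The only covariates it names are pain scores before treatment. The synopsis (Statistical Methods) makes the same split: t-test or Mann-Whitney for continuous variables in general, then "The impact of the PEA treatment on continuous outcome pain measures will be assessed using linear modelling". Neither place mentions quality of life.

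Outcome 4.3.7 is secondary: "To compare the change of quality of life between PEA/PLD and placebo treatment in women with surgical evidence of endometriosis", before surgery and again after it. Under section 5.4 the initial questionnaire covers "deep dyspareunia, dyschesia, daily pain and quality of life assessment", with physical and mental health as the quality-of-life domains. Sections 5.1 and 5.4 repeat the questionnaire at the end of the 8 weeks of treatment and 4 months after surgery. The baseline score needed for adjustment is therefore already collected.

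**The concern.** Read literally, the two method statements give pain a baseline-adjusted model and leave quality of life with an unadjusted comparison of change scores. The protocol gives no reason for the difference. Both are asked in the same questionnaire, of the same women, at the same times.

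A change score uses the baseline by subtracting it in full, which fixes the regression slope of follow-up on baseline at 1. A linear model estimates that slope. Where the true slope is not 1, the change score carries avoidable variance. Given a chance difference in baseline means between arms, it also carries part of that difference into the treatment estimate. At stake is the width of the confidence intervals, and the power, for one secondary outcome.

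**Working it through.** **The plan's own figure.** Section 8.1 takes "The sample size required for a one point difference on the numerical pain scale between PEA/PLD treatment and placebo" with "SD of 2 (based on a previous study performed by our team" and is "based on an alpha of 0.05, power of 0.8 and two sided p-value". The standardised effect is 1/2 = 0.5. The normal approximation gives 63 per arm; the t formula gives 63.77, so 64, as stated. Allowing for 30% drop-out and 30% without endometriosis, 64/(0.7 × 0.7) = 130.6, against the stated 130. The figures reproduce, but they concern pain, on the change from recruitment to 4 months after surgery. No quality-of-life figure is given.

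**Direction.** Let SDb and SDf be the baseline and follow-up SDs within arm, and ρ their correlation.

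- Variance of the change score: SDb² + SDf² − 2ρ·SDb·SDf.
- Residual variance after adjusting for baseline: SDf²(1 − ρ²).
- Difference: (SDb − ρ·SDf)².

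The difference is never negative. It is zero only when ρ·SDf = SDb, that is, when the true slope is 1. So, apart from the one degree of freedom spent on the slope, the adjusted model is never less precise.

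**Size with equal variances (an assumption).** The variance ratio, adjusted to change score, is (1 − ρ²)/(2(1 − ρ)) = (1 + ρ)/2. Borrowing 0.5 SD of change as the effect (also an assumption), power is approximately Φ(√(n/2) × 0.5/√ratio − 1.96). For example, with n = 64 and ρ = 0.5, √32 × 0.5/√0.75 − 1.96 = 1.306, so power is 0.904.

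Two sample sizes are relevant:

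- 4 months after surgery: 64 per arm, from section 8.1.
- Week 8: section 7.3 continues recruitment until 130 per group have the primary outcome, which precedes surgery. If 70% of these have endometriosis, 130 × 0.7 = 91 per arm.

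The n = 64 column uses the t distribution (125 df for the adjusted model); the n = 91 column uses the normal approximation.

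| Analysis | Variance ratio | Power, n = 64 | Power, n = 91 |
|---|---|---|---|
| Change score, unadjusted | 1 | 0.801 | 0.921 |
| Adjusted, ρ = 0.3 | 0.65 | 0.936 | 0.987 |
| Adjusted, ρ = 0.5 | 0.75 | 0.900 | 0.973 |
| Adjusted, ρ = 0.7 | 0.85 | 0.861 | 0.955 |
| Adjusted, ρ = 0.8 | 0.90 | 0.841 | 0.945 |

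The gain is about 4 to 13 points at n = 64 and about 2 to 7 points at n = 91. Simulation with normal data (4,000 runs, n = 64) at ρ = 0.3, 0.5 and 0.7 gives 0.80, 0.81 and 0.80 for the t-test on change, 0.78, 0.79 and 0.77 for Mann-Whitney on change, and 0.94, 0.90 and 0.85 for the adjusted model.

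**Size with unequal variances.** With SDf = 1.2 × SDb, the ratio is 1.44(1 − ρ²)/(2.44 − 2.4ρ):

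- ρ = 0.5: 1.08/1.24 = 0.87.
- ρ = 0.7: 0.7344/0.76 = 0.97.
- ρ = 0.8: 0.5184/0.52 = 1.00 (rounded).

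The gain then nearly vanishes at high ρ.

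**Chance imbalance.** Given a baseline difference D between arms, the change-score estimate is shifted by (slope − 1) × D. With 64 per arm the standard error of D is √(2/64) = 0.177 baseline SD. At slope 0.5, an imbalance of that size shifts the estimate by 0.5 × 0.177 = 0.09 baseline SD. The adjusted model removes this shift; averaged over randomisations it is zero in either analysis.

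**The case against.** The strongest objection is that this is detail for a statistical analysis plan. Section 8.2 is a short outline, only the protocol is at hand, and covariates for a secondary outcome are often settled later. A reader might infer that quality of life is barred from adjustment, or that no adjusted analysis of it will ever be done. The text supports neither: it names pain and does not say pain only. What stands is narrower. The protocol does state a general rule that covers quality of life, in two places, and a later plan that follows it would inherit the unadjusted test.

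A second objection is that the default is sound. Outcome 4.3.7 is a change, so baseline is already subtracted, and the comparison of randomised arms is valid. That stands in full. It would be wrong to say that baseline is ignored or that the unadjusted test is biased over randomisation. Only precision, and the shift conditional on an observed imbalance, are in question.

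A third objection concerns size. The effect and SD are borrowed from pain. The (1 + ρ)/2 ratio needs equal variances, and surgery falls between baseline and the last questionnaire, so equality there cannot be presumed. A figure of 64 per arm does not fit week 8. If the 130 in section 7.3 were all women with endometriosis, the change-score test would already have 98% power under the same assumption. These points also stand: they limit the size of the gain but do not reverse its direction.

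**Conclusion.** The point holds as an optional improvement. As written, 4.3.7 falls under an unadjusted comparison although its baseline score is collected, and a baseline-adjusted model would be at least as precise apart from one degree of freedom.

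The documents do not fix the size of the gain, because they give no quality-of-life effect, SD or correlation. Under the illustrative assumptions it is about 4 to 13 power points 4 months after surgery and about 2 to 7 at week 8, and it can shrink towards zero with a larger follow-up SD and a high correlation. A reader might take the first range as a power loss that the trial will suffer; the documents cannot support that. No stated figure is wrong, and neither the pain outcomes nor the sample size is affected.

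**What to change.** In section 8.2 and in the synopsis, widen the linear-model sentence so that it covers continuous pain and quality-of-life measures. For quality of life, model each domain's follow-up score at week 8 and at 4 months after surgery on arm and the baseline score of the same domain. The recruitment-site stratum used in randomisation (section 5.3) can be added as an optional covariate. Name this as the main analysis for 4.3.7, so that it is settled in advance which result counts if the adjusted and unadjusted comparisons differ.

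The cost is a small wording change in two places. It needs no new data, visits or participants.
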